### **6.6.2 Recent Memory Tasks** [AVLT, Arena Task, MST]

The recent memory measures include a verbal word list learning task (AVLT), a spatial navigation and learning measure (ARENA), and an object recognition memory task (MST). During post-intervention, the memory measure given as part of screening (Logical Memory Stories) will be repeated.

**6.6.2a. Description of the Auditory Verbal Learning Test (AVLT):** The AVLT is a word list learning task that assesses learning, proactive interference, along with retention and recognition over 30 minute delays (Rey, 1964; Schmidt, 1996). It is widely used in clinical settings and is similar to other word list learning tasks, except that the individual items are not semantically related to each other. Thus, participants must impose their own unique strategies in order to optimize learning. The AVLT consists of two 15 item lists, with List A given over 5 trials, followed by one presentation of List B, with subsequent immediate recall of List B, then List A. Later 30 minute recall and recognition of List A are obtained. The primary dependent variables for this task are overall learning, the degree of proactive interference, and delayed recall after 30 minutes.

**6.6.2b. Description of Computerized Arena Task** (Laurance et al., 2012): This is a task of spatial memory and navigation that has been linked to hippocampal function and is a human analogue to the Morris water maze used in animal studies. At UF, this task has been used in other IRB-approved studies with older adults (the VITAL study), those with Essential tremor, those with mild cognitive impairment and Alzheimer's disease.

[figure not shown]
The task is given on a computer and participants are trained in the use of a joystick or direction pad before beginning the task. Participants must navigate in a virtual, 3-D room displayed on a computer screen. They must start from different positions to find an invisible target on the

floor as quickly and efficiently as possible. Shown below are sample walls of the virtual room. The overall goal is to find a 'hidden target' on the floor of the arena.

[figure not shown]
The participant uses either a direction pad or joystick to navigate this "arena".

Navigation is constrained to a circular "arena" designed to look like a pool of water (the blue on the pictures above). The arena is bordered by a low wall and is in its entirety located in a perfectly square room, with each of the four

walls of the room differentiated from the others by 1-2 unique, fractal-based patterns

*Practice and Visible Target Trials.* The task begins by providing a participant with a 5-10 minute orientation session, in which they practice using the joystick or direction pad and then navigate to visible targets within the environment. In the figure to right the white elliptical circle represents the target. Performance on up to 5 visible-target navigation trials ends the practice session and the recorded path length and time to acquire the target will serve as a sensorimotor baseline against which invisible target trials will be evaluated.

*Hidden target condition.* After subjects have learned the task, they will participate in 8 invisible-target acquisition trials. In these trials the target is not visible from afar and is discoverable only when the joystick or direct pad icon is hovered over the target. A trial begins with a fixed tour of a new room, where each wall is shown for approximately 2 seconds during two sweeps of the room. Participants are instructed that the hidden target will be in the same place on each trial and that their task is to find it as soon as possible. Participants are typically given 120 seconds to find the target. During the first 2 trials, the examiner takes over after 120 seconds and assists the participant finding the target. No assistance is given after the initial two trials. If the target has not been located after 120 seconds in the later trials, the trial ends and a 10-second inter-trial interval (ITI) ensues, and the next trial begins. If the subject acquires the target on any trial, it becomes visible and a pleasant auditory signal additionally alerts them to target acquisition. They are allowed to stay on the acquired target for 15 seconds and are encouraged to rotate-in-place to survey the environment. After this, the 10-second ITI ensues and the next trial begins at a different compass point. A final spatial memory probe occurs following the 8th trial. On this final trial, the invisible target is removed unbeknownst to the participant. This means that target acquisition is not possible, but search behavior is evaluated with regard to the percent of the 120-second trial that is spent in the quadrant containing the target. On each acquisition trial, path length, time to acquire the target, and target acquisition (yes-no) are recorded. On the probe trial, path length and percent of time spent in each quadrant of the Arena is recorded. A composite score, consisting of mean z-scores on path length, time to acquire target, and percent of time spent in the proximal quadrant on the probe trial, will also be calculated. **The dependent variable will be this navigational performance composite.**

**6.6.2c. Description of the Mnemonic Similarity Test** (MST; Starke et al., 2013, 2015, 2017): This task is sensitive to hippocampal dysfunction and the effects of normal aging. It relies on process of pattern separation, the process of grouping similar inputs into distinct memory representations. The MST measures recognition memory performance for objects using traditional targets, novel foils, and other items (“lures”) that are perceptually and semantically related to the targets. During the learning/encoding phase, participants are shown a series of designs/objects. This is followed by a recognition task in which the items are true replications (hits), novel items (foils), or are similar but not identical to the hits (i.e., lures). The task is completed on a computer and takes about 15 minutes

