### **Parkinson Disease Group**

- Participants must have a diagnosis of idiopathic Parkinsons disease by a movement disorders specialist based on UK Brain Bank criteria (Hughes et al., 1992a, 1992b).
- No previous history of brain surgery (DBS, pallidotomy, thalamotomy, or fetal cell implants).
- No evidence of dementia based on scores on a cognitive screener (e.g., Dementia Rating Scale-2 (DRS-2) and score on delayed paragraph recall cannot be lower than 1.0 standard deviation of normative values
- May have difficulties with activities of daily living, but this is due to physical symptoms of Parkinson disease and not because of cognitive problems
- Unwillingness to undergo baseline and followup visits when they are 'off' standard dopamine medication
- Inability to undergo a brain scan

Additional exclusion criteria apply to those individuals who participate in the ***optional brain imaging*** study. The brain scan is optional for all participants except those with Parkinson disease. In that case, inability to undergo a brain scan, before and after intervention, is an exclusion. Exclusion criteria for a brain scan include

- Presence of claustrophobia
- Implants such as pacemakers, heart valves, brain aneurysm clips, orthodontics, non-removable body jewelry, or shrapnel containing ferromagnetic metal.

\*\*Note that we are highly experienced in working with older adults who are identified as experiencing current major depression or other psychological disturbances or who perform below cutoff on standard cognitive screening measures. The PI [[name]] is a boarded clinical neuropsychologist who has been working with this clinical population for over 30 years. The clinical Co-Is ([name], [name], [name], [name]) are experienced neurology clinicians, and the doctoral students on this protocol are clinical psychologists in training with experience in diagnosis and treatment of mood and cognitive disorders. Discussions will be held with individuals of concern and recommendations will be made to appropriate health care providers with permission of the participant and in line with standards of care.

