**Table 1: Screening & Baseline Measures**

Dementia Screen	Montreal Cognitive Assessment (MoCA: Nasreddine et al., 2005) or Dementia Rating Scale (DRS); these are widely used cognitive screening measures for dementia; See text for cutoff scores for Cognitively Normal and MCI groups
Objective Memory	Hopkins Verbal Learning Test-Revised and the WMS Logical Memory Stories : delayed recall scores on these measures are used to assign participants to Cognitively Normal (CN), amnestic and nonamnestic MCI groups, or to exclude Parkinson patients; (see text)
Other Cognitive measures	Executive Function - Trailmaking Test (Optional: Wisconsin Card Sort) (optional for PD) Visuospatial - Judgement of Line Orientation (JLO) (optional for PD) Language - Boston Naming Test, Category Fluency (optional for PD) Attention & Processing Speed - Digit Span, Digit Symbol (optional for PD)
Medical	Background medical history - rule out medical conditions (i.e., neurodegenerative, TBI, etc.),
	Charlson Comorbidity : Assesses for variety of comorbid medical conditions, computes risk factor score
	List of Medications : stable medications for 3 months; rule out use of anticholinergic medications; rule out use of photo-sensitive medications within 15 days of intervention
Psychiatric	Mental Health Screen V.3 (Carroll & McGinley) - this is modification of Structured Clinical Interview for DSM-IV psychiatric disorders, both current and historical (SCID-IV, First, Spitzer, Gibbon, & Williams); Goal is to rule out major depressive disorder, schizophrenia, psychosis, current substance abuse, and other Axis 1 disorders
Reading Literacy	Wechsler Test of Adult Reading (WTAR) or the reading subtest from the Wide Range Achievement Test –IV (WRAT-IV); participant reads aloud single words in order to estimate reading level; All must read on at least an 8 th grade level
Vision	Vision & Color Vision Screening : Basic visual acuity will be measured using a Snellen chart and color vision will be tested using Ishihara color plates.

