Participants will require a **Study Partner** (e.g., spouse, family member, friend) to provide independent information about their cognitive and behavioral status. The study partner will complete structured questionnaires about the participant. Both the participant and the study partner must provide independent consent for this to take place. The requirement for a study partner is 'optional' for those individuals with Parkinson disease.

It is possible that some participants, particularly those in the MCI or Parkinson groups who are recruited through the UF Cognitive Disorders and Dementia clinics or CMNDR, may have already had some of the screening measures, cognitive tasks, and rating scales associated with the current study. If so, we will request permission to use these, rather than repeat them, if they have been completed within 2 months. We will also request permission to access relevant medical and neuroimaging records.

If a participant does not meet inclusion/exclusion criteria, they will be thanked for their participation and given information as to the reason for their screen failure. There are several reasons why a participant might fail inclusion/exclusion criteria. Some that are of particular concern are poor test performance on the dementia screening measures (MoCA or DRS), presence of current major depression, substance abuse, or psychosis (i.e., hallucinations, delusions). If any of these scenarios emerge, we will discuss with the participant and, if appropriate, we will offer a referral for additional clinical evaluation through their primary physician or a specialty health care provider. Should individuals report suicidal ideation, the PI or co-investigators will meet with the participant to assess risk and refer for further evaluation

or treatment if necessary. With participant permission, we will provide results of our screening to their health care provider and/or them or a family member. As mentioned above, the project team is experienced in diagnosis and treatment of mood/cognitive disorders.

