## 6.6 Pre and Post-Intervention Measures

Participants who meet study criteria and who remain interested in participating in the 2 week intervention will be randomized to treatment or sham groups and undergo a baseline/ pre-intervention testing. The pre-intervention measures will be administered by a trained psychometrist or research assistant who will be blinded to group assignment (sham, real NIR stimulation).

The pre-intervention testing will take approximately 3 – 3.5 hours, and will consist of measures of executive function, recent memory, and mood. These same measures will be given after the two-week intervention has completed.

Individuals with Parkinson disease will complete the pre and post intervention visits when they are “off” their typical dopaminergic medications. This is identical to what Parkinson patients are asked to do as part of standard clinical care when seen at the UF Movement Disorders Clinic. To do so, the Parkinson patients will refrain from taking their parkinsonian medications overnight, with no dopa medication after 10:00 PM the night before. The theoretical rationale for evaluating patients when off dopamine medication is to obtain an index of the true status of their disease state.. The remainder of the protocol (i.e., screening, intervention) will be completed when participants are on their normal medications. When tested ‘off medication’, patients may experience increased slowness, tremors and stability. Because of this, they will be closely monitored and provided a wheel chair. If they become too uncomfortable they can take their medication and will be withdrawn from the study.

In previous IRB- approved studies, we have tested Parkinson patients off medication while they completed an array of cognitive, EEG, and other tasks. We have found that the tolerability was quite good and no participants dropped out of the study for the medication issue. In the current study, we are implementing testing ‘off dopa’ medications at the recommendation of the Parkinson Foundation.

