### 6.6.1 Executive Measures [NIH Examiner, Stroop]

The executive measures include the NIH Examiner, a computerized battery consisting of 9 individual subtasks described below, and a measures of cognitive inhibition (Stroop task). During post-intervention, an executive measure given as part of screening (Trail Making Test) will be repeated.

**6.6.1a Description of the NIH Examiner:** The National Institutes of Health Executive abilities: Methods for Neurobehavioral Evaluation and Research (Kramer et al., 2012). The NIH Examiner is a computer based battery that involves nine tasks of frontal-executive function and takes around 45 minutes to complete. Funding for development of the NIH Examiner was provided by NINDS in 2005 to develop sensitive, domain-specific tasks of fronto-executive function. The NIH Examiner consists of 9 individual tasks that can be combined into three domain specific scores: *Cognitive Control, Working Memory, and Fluency*. An overall *Executive Composite* score can also be computed (Kramer et al., 2014). In the current study, the **dependent variable for the primary aim will be the “executive composite”**

score calculated from the tasks within the NIH Examiner. Described below are each of the 9 tasks of the battery.

1. *Dot Counting (working memory)*: Participants look at a mixed array of green circles, blue circles, and blue squares. They are asked to count all of the blue circles and remember the final total, before counting the blue circles on new displays. The number of new displays increases from two to seven over a total of six experimental trials. The dependent variable is total correct score over trials 1-6, which contributes to the Executive Composite and the Working Memory factor scores.

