**fMRI.** We will perform an fMRI resting state block using echoplanar BOLD imaging (EPI) methods, with a TR of 2500ms, TE 16ms, field of view = 192mm, matrix = 64 and voxel size of 3.5mm^3. fMRI processing and analyses will use Statistical Parametric Mapping 12 (SPM12). We will present one ten minute block of resting state fMRI before and after intervention to provide insight into stimulation related change in functional networks. We will construct time series datasets implementing preprocessing methods to minimize physiological and motion artifact, with each volume assigned a condition based on task sequence. Whole-brain voxel-wise multiple regression analysis will verify activation patterns in resting state networks. Appropriate covariates, such as movement, for each participant's brain voxels will be included using the variation in BOLD signal over time. The REST toolbox and local specialized software will be used to obtain total interdependence (TI) values to assess functional connectivity between nodes in the resting state network, with particular focus on change in hippocampal connectivity. Primary dependent measures

will TI between each resting state ROI's per participant (FWE threshold  $p<.05$ ). TI values will compare intervention-related changes in functional connectivity.

Shown below is an overview of the temporal overview of the procedures.

Table 2: Overview of Procedures and Protocol

Measures	Pre-sceen	Screening	Base-line	Pre-MRI*	Intervention	Follow-up	Post-MRI*
Telephone Screening	X	X					
Inclusion / Exclusion		X					
Informed Consent		X					
Demographic Info		X					
Medical History		X					
MoCA or DRS-2		X					
HVLT-R or WMS-III LM		X				X	
Mental Health Screen V.3		X					
Charleson		X					
Medications		X					
WTAR or WRAT-IV		X					
Vision Screen		X					
Digit Span (WIT)		X					
TrailMaking Test			X			X	
Wisconsin Card Sort			x			x	
Digit Symbol (WIT)			X			X	
Category Fluency		X					
JLO		X					
Functional Activity Questionnaire (FAQ)			X				
Cognitive Function Inventory (CFI)			X			x	
Cognitive Function Inventory –Study Partner (not PD)			X				
Clinical Dementia Rating Scale -Study Partner (MCI group only)			X				
Demographic Info - Study Partner (Not PD)			X				
MRI Screener**		X*		X*			X*
Cognitive Change Index (CCI)			X			X	

Skintype Questionnaire			X			
Arena Task			X			X
AVTL			X			X
MST			X			X
NIH Examiner			X			X
Stroop			X			X
CalCap (processing speed)			X			X
UPDRS (PD only)			X			X

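### In Parkinson participants the Logical Memory pre score comes from on-medication screening and the post score from an off-medication visit, so within-arm change on this secondary measure cannot be interpreted, although the between-arm contrast stays unbiased

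*Protocol*

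**What the plan says.** - **Medication state.** Protocol section 6.6 has Parkinson participants attend the pre- and post-intervention visits off dopaminergic drugs, "with no dopa medication after 10:00 PM the night before". It then says: "The remainder of the protocol (i.e., screening, intervention) will be completed when participants are on their normal medications".
- **Timing of the test.** Section 6.6.2 says that post-intervention "the memory measure given as part of screening (Logical Memory Stories) will be repeated". In Table 2 (section 6.8) the row "HVLT-R or WMS-III LM" is marked at Screening and Follow-up and not at Baseline.
- **Use for eligibility.** Under the Parkinson criteria in section 6.4c, the "score on delayed paragraph recall cannot be lower than 1.0 standard deviation of normative values". Table 1 says of the HVLT-R and Logical Memory that "delayed recall scores on these measures are used to assign participants to Cognitively Normal (CN), amnestic and nonamnestic MCI groups, or to exclude Parkinson patients".
- **Reuse of clinic scores.** Section 6.5 allows earlier clinic results to replace screening tests "if they have been completed within 2 months". Sections 6.6 and 12 describe routine movement-disorder clinic visits as off medication.
- **Trail Making.** Section 6.6.1 says that "an executive measure given as part of screening (Trail Making Test) will be repeated", but Table 2 marks this test at Baseline and Follow-up.
- **Outcome tier and analysis.** Section 7.1 does not name Logical Memory. It falls among the other memory measures that are secondary. Section 7.3 plans a Group by Occasion mixed ANOVA within each cohort, change-score analyses, and analyses of predictors of change.

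**The concern.** A pre-post change is readable only if both scores are taken under the same conditions. For Logical Memory in the Parkinson cohort they are not. The first score is normally on medication, the second is off, and no off-medication score exists before the intervention. The first score is also the one that admitted the person, so some regression to the mean is built in.

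This sits badly with the rest of the protocol. Section 6.6 says the pre-intervention measures are the ones given again afterwards, and section 9 describes the post-treatment assessment as the same as the baseline visit. Reuse of clinic scores makes it less clear still, because the medication state of the pre score may then differ from one Parkinson participant to the next.

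The planned ANOVA reports an Occasion effect, and the change-score and predictor analyses use each person's change directly. All of these would mix medication state with whatever happened over the two weeks. Section 6.7.2 says the study is meant to determine potential effect sizes, so a misleading within-arm change could be carried forward to a later trial.

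**Working it through.** The protocol states no figure for this measure, so there is nothing to reproduce. The check traces the schedule and then sizes the effect under assumptions.

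**Schedule for Parkinson participants**

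| Measure | Pre score | Post score |
|---|---|---|
| NIH Examiner, Stroop, Arena, AVLT | Baseline, off | Follow-up, off |
| Trail Making, by Table 2 | Baseline, off | Follow-up, off |
| Trail Making, by section 6.6.1 | Screening, on | Follow-up, off |
| Logical Memory | Screening, on (or a clinic score up to 2 months old) | Follow-up, off |

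**Inputs.** From the protocol: 20 per arm (section 7.2.a) and a cut at -1.0 SD (section 6.4c). Assumed, because the protocol gives none: normal scores with unit SD, retest correlation r, an off-minus-on mean shift, and two-sided alpha of 0.05.

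**Regression to the mean**
- Mean of those admitted at z of -1 or above: φ(-1)/(1 - Φ(-1)) = 0.288 SD.
- Expected change from selection alone: -(1 - r) × 0.288, as follows.

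| r | 0.5 | 0.6 | 0.7 | 0.8 | 0.9 |
|---|---|---|---|---|---|
| Change (SD) | -0.144 | -0.115 | -0.086 | -0.058 | -0.029 |

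**Adding a medication shift** (20,000 simulated trials, r = 0.7, no intervention effect)

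| Assumed shift (SD) | Sham-arm change (SD) | Within-arm test rejects | Group by Occasion contrast (SD) | Its type I error |
|---|---|---|---|---|
| 0 | -0.09 | 8% | 0.00 | 5% |
| -0.2 | -0.29 | 36% | 0.00 | 5% |
| -0.5 | -0.59 | 91% | 0.00 | 5% |

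**Precision.** Suppose the response to being off medication varies between patients, with r = 0.7, a mean shift of -0.3 SD and a true effect of 0.6 SD. Power for the contrast is about 69% with no variation, 63% if the response SD is 0.3, and 53% if it is 0.5.

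**Gain from adjusting the post score for the screening score**
- Without selection, the residual variance is 1 - r² against 2(1 - r) for the change score. The ratio is (1 + r)/2: 0.90 at r = 0.8 and 0.80 at r = 0.6, so 10% to 20% smaller.
- With the Parkinson cut, the screening-score variance falls to 1 - 0.288 - 0.288² ≈ 0.63. The change-score variance is then (1 - r²) + (1 - r)² × 0.63.
- At r = 0.8 this gives 0.360 against 0.385, about 7% smaller. At r = 0.6 it gives 0.640 against 0.741, about 14% smaller.
- Adjustment does not remove the noise from varying drug response.

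**The case against.** The strongest reply is that the trial's hypothesis compares active with sham, and randomisation makes the medication shift and the regression to the mean equal in expectation in both arms. That stands: in every simulated scenario the contrast was centred on zero with the nominal error rate. It is also true that Logical Memory is an unnamed secondary measure, and that the co-primary measures are taken at both off-medication visits.

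Several stronger readings are tempting, but the documents do not support them:

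- **That the medication switch biases the estimated effect of NIR.** It does not, for the reason just given.
- **That precision collapses.** If the retest correlation fell from 0.8 to 0.6, the difference detectable with 20 per arm at 80% power would rise from 0.909 × √0.4 = 0.57 SD to 0.909 × √0.8 = 0.81 SD. Nothing in the protocol supports that drop. If varying drug response alone supplied the extra variance of 0.40, its SD would have to be about 0.63.
- **That selection produces a large shift throughout MCI.** Truncating a normal reference population at -1.5 SD gives a mean of -1.94 SD and an apparent gain of 0.39 to 0.78 SD for r of 0.8 to 0.6. At most this fits amnestic participants admitted on paragraph recall. Section 6.4c also allows entry on the HVLT-R, requires a partner-confirmed complaint and a CDR of 0.5, and requires normal memory for nonamnestic MCI. MCI participants have no medication switch.
- **That Trail Making has the same defect.** Table 2 places it at Baseline, so the conflict with section 6.6.1 may be one of wording only.

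The unseen statistical analysis plan may already adjust for the screening score. It cannot supply an off-medication pre score that was never collected.

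**Conclusion.** The point holds, with limited reach. In the Parkinson cohort, the Occasion effect, within-arm changes and predictor-of-change analyses for Logical Memory mix medication state and selection with any change over the intervention. The selection part is slight, about 0.03 to 0.14 SD for assumed retest correlations of 0.9 to 0.5. The medication part cannot be sized from the protocol. If it were 0.2 to 0.5 SD, it would be enough to make within-arm tests misleading. Precision of the between-arm contrast falls only to the extent that drug response varies between patients. Amnestic MCI participants admitted on low paragraph recall would also drift upward in both arms, by an amount that depends on assumptions. The between-arm contrast is unbiased in expectation, and the NIH Examiner, Stroop, Arena and AVLT are not affected.

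**What to change.** 1. Reconcile sections 6.6, 6.6.2 and 9 and Table 2 on when, and in which medication state, the Logical Memory pre score is taken. Cover reused clinic scores (section 6.5). Reconcile section 6.6.1 with Table 2 on Trail Making.
2. For Logical Memory, replace the Group by Occasion ANOVA and the change score with a between-arm comparison of the post score adjusted for the screening score, and state that within-arm change will not be interpreted. This uses data already planned and costs only a change of wording.
3. Alternatively, also score the test at the existing baseline visit, under the conditions the protocol already sets for that visit. Use that score as the pre value and keep the screening score for eligibility only. The cost is added time in a visit of 3 to 3.5 hours and one more exposure to the stories, equal in both arms.
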